#### **7.4 CRITERIA FOR TREATMENT CONTINUATION**

Patients may continue treatment with lorbinecetin as long as no unacceptable toxicity and/or PD occurred, and for a maximum of three cycles. Thereafter, treatment with lorbinecetin can continue under a Compassionate Use Agreement.

**In Part A and Part B, patients assigned to Sequence 1 (TR) (lorbinecetin + itraconazole in Cycle 1),** after Cycle 1 the administration of a new cycle should be delayed if the criteria in [Table 7](#) are not met on the corresponding Day 1. Re-assessments will be performed periodically at intervals of at least 72 hours but not more than one week. Lorbinecetin administration should be delayed until recovery of these parameters. A maximum delay of 14 days from the theoretical due date will be allowed for recovery from treatment-related AEs. If recovery has not occurred after that period, the patient should discontinue the treatment, except in case of obvious patient benefit at the criteria of the Investigator and upon agreement with the Sponsor.

**In Part B, patients assigned to Sequence 2 (RT) (lorbinecetin + itraconazole in Cycle 2),** criteria for treatment continuation should be investigated on Day 15 of Cycle 1 in order to confirm itraconazole administration start on Day -4 of Cycle 2, assuring that the continuation criteria will be finally met on Day 1 of Cycle 2 assessment. In case of detected abnormalities on Day 15 in sequence RT, these assessments should be repeated every 48-72 hours until recovery to retreatment criteria. Initiation of itraconazole will be delayed for a maximum of 14 days to ensure that pre-treatment with itraconazole is fulfilled. If recovery has not occurred after that period, the patient should discontinue the treatment, except in case of obvious patient benefit at the criteria of the Investigator and upon agreement with the Sponsor.

Re-treatment criteria for lorbinecetin administration should be met on Day 1 of Cycle 2.

Any patient having any grade  $\geq 3$  laboratory abnormalities and/or treatment-related AEs after Cycle 2 or Cycle 3 is suggested to have the relevant tests re-assessed at intervals of at least 72 hours but not more than one week.

If they were not met, treatment will be delayed for a maximum of 2 days to evaluate continuation of lorbinecetin administration, with re-treatment criteria being checked every 24 hours. During this time the patient will continue receiving itraconazole. If

after 2 days of delay the patient does not meet the criteria for treatment continuation, itraconazole will be stopped and the patient will be considered not evaluable for the trial.

If the criteria for treatment continuation are not met as described above, treatment must be discontinued and the EOT visit performed.

**Table 7.** Criteria for lorbinecetin treatment continuation.

Variable	Lorbinecetin (Day 1)
ECOG PS	$\leq 1$
ANC	$\geq 1.5 \times 10^9/L$
Platelets	$\geq 100 \times 10^9/L$
Hemoglobin a	$\geq 8.0 \text{ g/dL}$
Total bilirubin	$\leq 1.0 \times \text{ULN}$ . If it is $> 1.0 \times \text{ULN}$ but $\leq 1.5 \times \text{ULN}$ , direct bilirubin must be $\leq 1.0 \times \text{ULN}$
Albumin	$\geq 3.0 \text{ g/dL}$
AST/ALT	$\leq 3.0 \times \text{ULN}$
CPK	$\leq 2.5 \times \text{ULN}$ ( $\leq 5.0 \times \text{ULN}$ is acceptable if elevation is disease-related)
Serum Creatinine levels/ Calculated CLcr (Cockcroft and Gault's formula)	Serum creatinine levels $\leq \text{ULN}$ or calculated CLcr $\geq 30 \text{ mL/min}$ , if abnormal ( $>\text{ULN}$ ) serum creatinine levels
Other non-hematological drug-related AEs (except increased AP, or grade 2 alopecia, asthenia, and non-optimally treated nausea and/or vomiting) b	Grade $\leq 1$

a Patients may receive PRBC transfusions and/or EPO treatment if clinically indicated to increase/maintain adequate hemoglobin levels.

b Any grade allowed for increased GGT and up to grade 2 allowed for neuropathy.

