Variable	Day 1																		
ECOG PS	$\leq 1$																		
ANC	$\geq 1.5 \times 10^9/l$																		
Platelets	$\geq 100 \times 10^9/l$																		
Hemoglobin a	$\geq 8.0 \text{ g/dl}$																		
Total bilirubin	$\leq 1.0 \times \text{ULN}$ . If it is $> 1.0 \times \text{ULN}$ but $\leq 1.5 \times \text{ULN}$ , direct bilirubin must be $\leq 1.0 \times \text{ULN}$																		
Albumin	$\geq 3 \text{ g/dl}$																		
AST / ALT	$< 3.0 \times \text{ULN}$																		
CPK	$\leq 2.5 \times \text{ULN}$ ( $\leq 5.0 \times \text{ULN}$ is																		

		acceptable if elevation is disease-related)
	Serum Creatinine levels/ Calculated CLcr (Cockcroft and Gault's formula)	Serum creatinine levels $\leq$ ULN or calculated CLcr $\geq$ 30 mL/min, if abnormal ( $>$ ULN) serum creatinine levels
	Other non-hematological drug-related AEs (except increased AP, or grade 2 alopecia, asthenia, and not optimally treated nausea and/or vomiting) b	Grade $\leq$ 1

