
a Patients may receive PRBC transfusion and/or EPO treatment if clinically indicated to increase/maintain adequate hemoglobin levels.
 
b Any grade accepted for increased AP.
 
Sequence 1 (TR): If a patient does not meet the requirements for treatment continuation on Day 1 of further cycles, treatment will be withheld until recovery for a maximum of 14 days after the theoretical treatment date. If recovery has not occurred after a delay of <math>></math> 14 days, discontinue treatment (except in case of obvious patient benefit at the criteria of the Investigator and upon agreement with the Sponsor).
 
Sequence 2 (RT): If a patient does not meet the requirements for treatment continuation on Day 15 of Cycle 1, treatment with itraconazole will be withheld until recovery for a maximum of 14 days after the theoretical treatment date. If recovery has not occurred after a delay of <math>></math> 14 days, discontinue treatment (except in case of obvious patient benefit at the criteria of the Investigator and upon agreement with the Sponsor).
 
If a patient does not meet the requirements for treatment continuation on Day 1 of Cycle 2, treatment with lurbinectedin will be withheld until recovery for a maximum of 2 days after the theoretical treatment date. During this time, the patient will continue receiving itraconazole. If recovery has not occurred after a delay of <math>></math> 2 days, itraconazole will be stopped and the patient will be considered not evaluable for the trial.
 
AEs, adverse events; ALT, alanine aminotransferase; ANC, absolute neutrophil count; AP, alkaline phosphatase; AST, aspartate aminotransferase; CLcr, creatinine clearance; CPK, creatine phosphokinase; ECOG PS, Eastern Cooperative Oncology Group Performance Status; EPO, erythropoietin; PRBC, packed red blood cells; ULN, upper limit of normal.
		

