## **5.3 REPLACEMENT OF PATIENTS**

Patients must be replaced if they are not evaluable for the assessment of the primary endpoint (e.g., if they have not sufficient and interpretable PK parameters).

Evaluable patients for Part A should have completed sufficient study procedures until Day 8 of Cycle 1 (i.e., most itraconazole administration and PK assessments). Evaluable patients for Part B for the main objective of the study (e.g., assessment of lubrinezdin PK) should have provided sufficient and interpretable PK parameters (e.g.,  $AUC_{0-t}$

should cover at least 80% of  $AUC_{0-\infty}$ ) of Cycle 1 and 2. Evaluable patients should have received the first two complete cycles regardless dose delays or reductions.

For Part A and Part B, the compliance of itraconazole will be confirmed based on a patient's diary, the drug accountability and the expected individual plasma concentration at the steady state.

Any replacement patient during the treatment phase will be given a new patient number and assigned to the same sequence as the not-evaluable patient being replaced. All replaced patients who received the study treatment were to be included in the general safety.

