**Sequence 1 (TR):**

If a patient does not meet the requirements for treatment continuation on Day 1 of further cycles, treatment will be withheld until recovery for a maximum of 14 days after the theoretical treatment date. If recovery has not occurred after a delay of  $> 14$  days, discontinue treatment (except in case of obvious patient benefit at the criteria of the Investigator and upon agreement with the Sponsor).

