**Sequence 2 (RT):**

If a patient does not meet the requirements for treatment continuation on Day 15 of Cycle 1, treatment with itraconazole will be withheld until recovery for a maximum of 14 days after the theoretical treatment date. If recovery has not occurred after a delay of  $> 14$  days, discontinue treatment (except in case of obvious patient benefit at the criteria of the Investigator and upon agreement with the Sponsor).

If a patient does not meet the requirements for treatment continuation on Day 1 of Cycle 2, treatment with lorbinecetin will be withheld until recovery for a maximum of 2 days after the theoretical treatment date. During this time, the patient will continue receiving itraconazole. If recovery has not occurred after a delay of  $> 2$  days, itraconazole will be stopped and the patient will be considered not evaluable for the trial.

AEs, adverse events; ALT, alanine aminotransferase; ANC, absolute neutrophil count; AP, alkaline phosphatase; AST, aspartate aminotransferase; CLcr, creatinine clearance; CPK, creatine phosphokinase; ECOG PS, Eastern Cooperative Oncology Group Performance Status; EPO, erythropoietin; PRBC, packed red blood cells; ULN, upper limit of normal.

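### Synopsis Table S2 and body Table 7 set different re-treatment criteria (GGT, neuropathy and, at the boundary, AST/ALT), and nothing says which table prevails

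*Protocol*

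**What the plan says.** The criteria for starting a new lurbinectedin cycle appear twice in the protocol: in the synopsis as Table S2 and in Section 7.4 as Table 7. The two tables have the same title and govern the same Day 1 decision. The synopsis text delays the next cycle when Table S2 is not met; the matching sentence in Section 7.4 refers to Table 7. The SAP does not restate the criteria.

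Both tables end with a row that limits other non-hematological drug-related adverse events to grade 1 or less. The exemptions in the row label are the same in substance. Table S2 has "except increased AP, or grade 2 alopecia, asthenia, and not optimally treated nausea and/or vomiting" and Table 7 has "except increased AP, or grade 2 alopecia, asthenia, and non-optimally treated nausea and/or vomiting". Footnote b, attached to that row, differs:

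- Table S2: "Any grade accepted for increased AP"
- Table 7: "Any grade allowed for increased GGT and up to grade 2 allowed for neuropathy"

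The consequences of failing are set by sequence. In Sequence 1, "treatment will be withheld until recovery for a maximum of 14 days after the theoretical treatment date"; after that the patient discontinues, unless there is obvious benefit and the sponsor agrees. In Sequence 2, the criteria are first checked on Day 15 of Cycle 1, before itraconazole starts. If they are then not met on Day 1 of Cycle 2 and remain unmet after a delay of 2 days, "itraconazole will be stopped and the patient will be considered not evaluable for the trial".

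Section 5.3 adds: "Evaluable patients should have received the first two complete cycles regardless dose delays or reductions" and "Patients must be replaced if they are not evaluable for the assessment of the primary endpoint".

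**The concern.** These tables are working rules. A site uses them to decide whether a patient receives a second dose of a cytotoxic drug. If they disagree, the same patient on the same day can be fit for re-treatment under one and unfit under the other, and a site following either is following the protocol.

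The statistical stake is membership of the analysis set. The primary comparison uses Part B patients who complete both cycles, so a rule that decides who receives Cycle 2 also decides who can enter it. Delays and dose reductions are affected too, because Section 7.5 makes a treatment-related delay of more than one week a trigger for dose reduction. Consistent coding of protocol deviations is also at risk: SAP Section 7.2 has a category for patients treated on after meeting withdrawal criteria, and that category cannot be applied uniformly under two rule sets.

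**Working it through.** No arithmetic applies. The check is a row-by-row comparison of Table S2 (Synopsis, Criteria for Treatment Continuation) with Table 7 (Section 7.4), followed by the outcome for each patient type.

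**Step 1: compare the rows.** Eight rows have the same limits: ECOG PS, ANC, platelets, hemoglobin, total bilirubin, albumin, CPK, and creatinine/CLcr. The rest compare as follows.

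| Item | Table S2 | Table 7 |
|---|---|---|
| AST/ALT | < 3.0 × ULN | ≤ 3.0 × ULN |
| Increased GGT | no allowance; grade ≤ 1 applies if it is a drug-related AE | any grade (footnote b) |
| Neuropathy | no allowance; grade ≤ 1 applies | up to grade 2 (footnote b) |
| Increased AP | exempt in row label; any grade (footnote b) | exempt in row label, no grade limit; footnote silent |

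**Step 2: classify a patient who meets every other criterion.**

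| Finding at the check | Table S2 | Table 7 |
|---|---|---|
| Drug-related neuropathy, grade 2 | fails | passes |
| GGT increase, grade ≥ 2, counted as a drug-related AE | fails | passes |
| AST or ALT exactly 3.0 × ULN | fails | passes |
| Increased AP, any grade | passes | passes |

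Three items change the decision, and in each Table S2 is the stricter. AP does not change it.

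**Step 3: follow the consequence.**

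- *Sequence 1.* Failing on Day 1 of Cycle 2 means a delay of up to 14 days, then discontinuation unless the exception applies. A patient who discontinues there has not received two complete cycles and so is not evaluable under the Part B rule in Section 5.3.
- *Sequence 2, Day 15 of Cycle 1.* The criteria are checked before itraconazole starts. Failing means repeat checks every 48 to 72 hours and a delay of up to 14 days in starting itraconazole, with the same exception after that. The choice of table already matters here.
- *Sequence 2, Day 1 of Cycle 2.* A finding that appears or worsens after the Day 15 check, and does not recover within 2 days, makes the patient not evaluable under Table S2. Under Table 7 the same patient is dosed.

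**Step 4: look for a precedence rule.** Nothing in the protocol says whether the synopsis or the body prevails.

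**The case against.** The strongest reply is that the conflict will rarely bite.

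- **Neuropathy.** Inclusion criterion 6 requires recovery to grade 1 or less from earlier drug-related events, with exceptions only for alopecia and asthenia or fatigue. Drug-related grade 2 neuropathy would therefore normally have to arise on study, within one or two cycles. The background names myelosuppression as the most relevant toxicity and gives no neuropathy rate.
- **GGT.** The row concerns adverse events. Section 8.5.1 restricts when a laboratory abnormality is recorded as one, although Section 8.4.1 adds the investigator's view of clinical relevance. An isolated GGT rise may never reach the row. One trigger in Section 8.5.1 is a dosing delay, which itself depends on the table used, so some circularity remains.
- **Sequence 2.** A persistent abnormality would normally be found on Day 15, before the 2-day rule can apply.

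All of this stands as a limit on frequency. None of it removes the contradiction. A claim that Section 7.4 prevails because it is the body of the protocol has no support in the text.

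A reader might also infer more than the documents support:

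- *That AP changes the decision.* Both row labels exempt increased AP without a grade limit. The footnote difference is one of wording only.
- *That each patient classified differently costs 1 of 8, or 12.5%, of the primary comparison.* That is the weight of one patient among eight. Section 5.3 requires replacement, in the same sequence, so the planned eight evaluable patients are kept.
- *That the Test/Reference ratio is biased, or that sites are using different tables.* The documents show neither. They show only that different use is possible at the approximately two planned sites.

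**Conclusion.** The point holds in a limited form. The protocol states two sets of criteria for one re-treatment decision, and they conflict. GGT and neuropathy are the substantive items; AST/ALT matters only at the single value 3.0 × ULN. This is an internal contradiction in the current text, wrong as written, rather than a design choice on which opinions may differ.

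The effect is on who is re-dosed, delayed or discontinued, on which patients enter the Part B comparison, and on consistency between sites. It does not reduce the planned number of evaluable patients. How often it would occur cannot be estimated, because the documents give no rate for drug-related neuropathy or GGT increase after one cycle. For GGT, the conclusion assumes that the rise is treated as a drug-related adverse event. No view is taken here on which limits are clinically right.

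**What to change.** Reconcile Table S2 and Table 7 so that every row, footnote b and the AST/ALT limit are identical, and align the AP wording at the same time. The clinical team must decide which values apply. Until the corrected text is in force, state in writing which table governs, and tell the sites.

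The cost is a protocol clarification or amendment and a note to sites. Sample size, randomization and the analysis model are unaffected.

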**Sequence 1 (TR):**

If a patient does not meet the requirements for treatment continuation on Day 1 of further cycles, treatment will be withheld until recovery for a maximum of 14 days after the theoretical treatment date. If recovery has not occurred after a delay of  $> 14$  days, discontinue treatment (except in case of obvious patient benefit at the criteria of the Investigator and upon agreement with the Sponsor).

**Sequence 2 (RT):**

If a patient does not meet the requirements for treatment continuation on Day 15 of Cycle 1, treatment with itraconazole will be withheld until recovery for a maximum of 14 days after the theoretical treatment date. If recovery has not occurred after a delay of  $> 14$  days, discontinue treatment (except in case of obvious patient benefit at the criteria of the Investigator and upon agreement with the Sponsor).

If a patient does not meet the requirements for treatment continuation on Day 1 of Cycle 2, treatment with lorbinecetin will be withheld until recovery for a maximum of 2 days after the theoretical treatment date. During this time, the patient will continue receiving itraconazole. If recovery has not occurred after a delay of  $> 2$  days, itraconazole will be stopped and the patient will be considered not evaluable for the trial.

AEs, adverse events; ALT, alanine aminotransferase; ANC, absolute neutrophil count; AP, alkaline phosphatase; AST, aspartate aminotransferase; CLcr, creatinine clearance; CPK, creatine phosphokinase; ECOG PS, Eastern Cooperative Oncology Group Performance Status; EPO, erythropoietin; PRBC, packed red blood cells; ULN, upper limit of normal.

## 7.5 DOSE REDUCTION

Patients may continue in the study treatment at a lorbinecetin reduced dose if they present any of the following:

- Grade 4 thrombocytopenia or grade 3 thrombocytopenia concomitantly with grade  $\geq 3$  bleeding.
- Two dose delays or prolonged ( $>$  one week) dose delay due to treatment-related adverse events.

- Grade  $\geq 3$  treatment related non-hematological toxicity. Exceptions are: grade  $\geq 3$  nausea and/or vomiting not optimally treated, grade 3 fatigue lasting < two days, grade 3 diarrhea lasting < one day or non-optimally treated, isolated grade 3 transient ALT/AST elevations which are rapidly reversible and not leading to subsequent delays, and non-clinically relevant isolated biochemical abnormalities.
- Grade 4 neutropenia or any grade febrile neutropenia.

Up to two dose reductions are allowed per patient. Patients who continue to experience treatment-related toxicity and/or dose delays after two dose reductions must be withdrawn from the study. Once the dose has been reduced for an individual patient, it will not be re-escalated under any circumstances.

Lurbinectedin dose reduction levels are shown in [Table 8](#).

**Table 8.** Levels of (intra-patient) lurbinectedin dose reduction in subsequent cycles in Part A and B.

Dose reduction	Lurbinectedin (q3wk) (mg/m  )	
	Lurbinectedin alone	Itraconazole co-administration cycle
1 (starting dose)	3.2	0.8
-1	2.6	0.6
-2	2.0	-

Lurbinectedin total doses in mg will be rounded to the first decimal, if necessary.  
q3wk, every three weeks.

Patients who experience any treatment-related grade 3/4 hypersensitivity and/or extravasation reactions will permanently discontinue treatment.

## 7.6 CONCOMITANT MEDICATION

All treatments received by the patient during the on-treatment period of the trial must be documented in the eCRF.

### 7.6.1 Allowed Medications/Therapies

- Therapies for pre-existing and treatment-emergent medical conditions, including pain management and local management of mucositis/stomatitis.
- Blood products and transfusions, as clinically indicated.
- Bisphosphonates.
- In case of nausea or vomiting, extended symptomatic treatment for emesis will be allowed (with the exception of aprepitant equivalent agents).
- Erythropoietin treatment according to the ASCO guidelines.
- Low-molecular weight heparin (LMWH) and/or any other anticoagulants, as clinically indicated. Oral anticoagulants must be carefully monitored.
- Treatment or secondary prophylaxis with granulocyte colony-stimulating factors G-CSF according to ASCO guidelines.
- CNS irradiation if required, and/or limited field bone radiotherapy for pain control outside the thoracic wall.
- Megestrol acetate for wasting syndrome.

- Contraceptives.

### 7.6.2 Prohibited Medications/Therapies

- Concomitant administration of any other antineoplastic therapy.
- Any other investigational agents.
- Immunosuppressive therapies other than corticosteroids for antiemetic prophylaxis, pain control, or low-dose replacement in patients requiring this approach.
- Aprepitant or any other NK-1 antagonist or related Substance P-antagonists (except rolapitant).
- Primary G-CSF prophylaxis.
- CYP3A4 inhibitors such as ketoconazole, fluconazole, voriconazole, telithromycin, clarithromycin, erythromycin, naftillin, aprepitant, fosaprepitant, verapamil, modafinil, nefazodone, or grapefruit juice.
- CYP3A enzyme inducers and/or inhibitors (unless strictly necessary and when there is no therapeutic alternative treatments) (see [Appendix 3](#)).
- Use of any prescription or non-prescription herbal and/or dietary supplements within 14 days prior to the first dose of study medication and until 31 days after the last administration of lurbinecetin, unless the Investigators, with the Sponsor agreement, consider it will not interfere with study procedures of patient safety.

### 7.6.3 Drug-Drug Interactions

*In vitro* studies with human microsomes have shown that CYP3A4 is the major CYP isoform involved in the metabolism of lurbinecetin. The estimated contribution of the other CYP isoenzymes to the lurbinecetin metabolism is considered to be negligible. Therefore, concomitant drugs which induce or inhibit any of these cytochromes, especially CYP3A4, should be carefully monitored or avoided, whenever is possible.

A potentially significant interaction with aprepitant is suggested by available phase II data from ovarian cancer patients and phase I data from the PM1183-A-008-13 study. Lurbinecetin clearance was reduced by around 30%, approximately, in the presence of aprepitant. Although all patients eventually recovered, the use of aprepitant is currently forbidden in all phase II/III lurbinecetin studies.

